**Figure 1: Study Schema**

PM= Pegcetacoplan Monthly; SM= Sham Monthly; PEOM= Pegcetacoplan Every-Other-Month; SEOM= Sham Every-Other-Month

### 3.2. Randomization

Subjects will be randomized 2:2:1:1 using a web-based randomization system to receive treatment with PM, PEOM, SM or SEOM, respectively.

The randomization scheme will be maintained by the Sponsor, or designee. Subject randomization will be stratified by GA lesion area at screening based on assessment from the reading center ( $< 7.5 \text{ mm}^2$ ;  $\geq 7.5 \text{ mm}^2$ ) and presence of CNV in the fellow eye (yes; no).

### 3.3. Masking

This is a double-masked study. Designated masked study site staff (e.g., assistant(s), VA technicians, optical coherence tomography (OCT) technicians, photographers, technicians administering questionnaires, subjects, Reading Center personnel, the assigned evaluating physician(s), and the Sponsor) will be masked to treatment assignment. However, the treating physician and any associated support staff involved in performing the intravitreal or sham injections will be unmasked to study treatment. These individuals are only responsible for administering the study drug and are not involved in assessing adverse events. In addition, the unmasked individuals are not allowed to discuss treatment and/or subject outcomes with masked study staff, including the evaluating physician. The Principal Investigator must be masked to subjects' treatment assignment. To prevent bias in treatment assignment, eligible subjects will be randomized using a web-based randomization system. Processes and plans will be put in place to avoid unintentional unmasking during the study. All study roles will be clearly documented on the site delegation of authority log and once the roles have been designated and executed, these roles should not be switched during the conduct of the study. In unforeseen circumstances, a site can contact the Sponsor to switch a study staff member from the masked role to the unmasked role but not vice versa. Details on unmasking at the Month 12 reporting are in Section 3.5.

While the actual study treatment (pegcetacoplan vs. sham) is masked, the treatment frequency (monthly vs. every other month) for each individual subject is known.

### 3.4. Sample Size and Power Considerations

A total of approximately 600 subjects will be randomized in a 2:2:1:1 ratio to receive treatment with PM, PEOM, SM, or SEOM. The annual growth rate in GA lesion area is expected to have a mean of 1.47, 1.70 and 2.13  $\text{mm}^2/\text{year}$  for PM, PEOM and Sham-Pooled (Sham) groups, respectively, as estimated from the results of a Phase 2 trial of pegcetacoplan. The standard deviation of the lesion growth is estimated to be 1.50  $\text{mm}^2$  based on the same Phase 2 trial data or 1.25  $\text{mm}^2$  based on natural history data (Holekamp N, 2019).

The power of the study for the primary endpoint is presented in Table 1 for sample size of 200 in each treatment arm. The approximation is calculated using PROC POWER ONEWAYANOVA, Statistical Analysis System (SAS) 9.4. The study power for the primary endpoint is likely larger when utilizing the longitudinal data to model the primary endpoint. The actual study power for the primary endpoint may also vary based on the distribution of the stratification factors (i.e., lesion area at screening, presence of CNV in fellow eye). Study power was not calculated for key secondary functional endpoints.

**Table 1: Power to Detect a Difference among Three Groups with an Equal Size of 200 Subjects**

Common Standard Deviation (mm  )	Alpha (two-sided)	Power for a true mean of 1.47, 1.70, and 2.13 mm  /year for PM, PEOM and Sham, respectively		
		PM vs Sham	PEOM vs Sham	Overall (Among 3 groups)
1.25	0.0495	> 99.9%	92.9%	99.9%
1.25	0.0248	99.9%	88.2%	99.7%
1.40	0.0495	99.7%	86.5%	99.3%
1.40	0.0248	99.3%	79.4%	98.6%
1.50	0.0495	99.2%	81.5%	98.4%
1.50	0.0248	98.4%	73.1%	97.0%

PM = pegcetacoplan Monthly, PEOM = pegcetacoplan Every-Other-Month; Sham = Sham Monthly + Sham Every-Other-Month

### 3.5. Analysis Timing and Unmasking

The analysis of data from the first 12 months of the study will be performed when all subjects have completed the Month 12 visit in the study or discontinued early and all corresponding data have been entered into the database, reviewed, cleaned, and finalized as the Month 12 dataset per the 12-Month Primary Analysis Data Cut Plan and the Programming Plan. At the time of the analysis of the Month 12 dataset, subjects who have not completed or discontinued from the study will still be followed by the sites as part of the second year.

At the time of the Month 12 reporting, Sponsor personnel who are analyzing, interpreting, and reporting data from the Month 12 dataset will be unmasked to treatment assignment. To maintain data integrity for the remainder of the study, sponsor and contract research organization (CRO) personnel responsible for continuing study oversight will remain masked as documented in the Study Masking Plan and the GA Internal Unmasking Plan.

Analyses will include formal hypothesis testing of the primary efficacy endpoint at Month 12. Key secondary, secondary, and exploratory endpoints will be evaluated based on the Month 12 dataset in a descriptive manner. An analysis of the safety data in the Month 12 dataset will also be performed.

The final study reporting will be based on data after all subjects have either completed the Month 24 visit in the study or discontinued the study early, and all data from the study are entered in the database and the database is reviewed, cleaned, and locked as the final dataset. Minor changes are expected from the Month 12 dataset (e.g. adverse event end dates for events ongoing in the Month 12 dataset), however, all subsequent differences in data prior to the Month 12 visit will be listed. Analysis of the final dataset will include testing of hypotheses of the key secondary endpoints at Month 24 as described in Section 6.3.1. A cumulative analysis of all data through the end of the study will be produced based on the final dataset.

Aggregate results of the Month 12 reporting may be reported before completion of the study. However, subjects, masked study site personnel, masked CRO personnel at Covance, Sponsor team members with study oversight responsibility, and central reading center personnel will remain masked to individual treatment assignments until after the study is completed

(after all subjects have either completed Month 24 or discontinued early from the study), the database is locked and the unmasking has been approved.

### **3.6. Definition of 12-Month Data in the Month 12 Dataset**

All screening and post-baseline data with a clinical date (i.e., administration/assessment/onset/start date) on or before the defined Month 12 data cutoff date will be included in the Month 12 Dataset. The 12-month data cutoff will include all data regardless of the type of study visit at which it was collected. This may include data collected at unscheduled visits or early termination visits if the visit date was on or before the 12-month data cutoff date. The Month 12 data cutoff is defined as:

#### All data except microperimetry

- If the subject completed Month 12 (Visit 14) assessments, then the data cutoff will be the day that the Month 12 (Visit 14) assessments are completed, regardless of Study Day.
- If the subject did not complete the Month 12 (Visit 14) assessments (e.g. missed or early terminated) then Study Day 375 (Study Day 360 (target date) + 15) will be used as the Month 12 cutoff.

#### Microperimetry

- Study Day 450 (Study Day 360 (target date) + 90) will be used as the Month 12 cutoff. This is to allow any unscheduled assessments including repeated microperimetry assessments collected as of the Month 12 datacut date to be considered for the Month 12 analysis visit according to the analysis visit windowing algorithm as specified in Section [13.4.2](#)

## **4. STATISTICAL ANALYSIS SETS**

Two sham treatment arms (SM and SEOM) will be pooled into a single control (Sham) group for analyses.

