This is a 24-month, Phase 3, multicenter, randomized, double-masked, sham-injection controlled study to assess the efficacy and safety of multiple IVT injections of pegcetacoplan in subjects with GA secondary to AMD.

The study will randomize approximately 600 subjects across approximately 100 multinational sites. Subjects will be screened within 28 days before receiving pegcetacoplan or sham injection. Upon entry into the study, subjects will be assigned a screening number. Subjects who meet all inclusion and none of the exclusion criteria will return to the clinic for randomization and treatment on Visit 2 (Day 1). At this visit, subjects will be randomized 2:2:1:1 to

receive pegcetacoplan monthly, pegcetacoplan every other month, sham injection monthly, or sham injection every other month, respectively. Randomization will be stratified according to GA lesion area at screening ($< 7.5 \text{ mm}^2$; $\ge 7.5 \text{ mm}^2$), and presence of CNV in the fellow eye.

All subjects will be assessed monthly during the first 12 months regardless of treatment regimen. From Month 12 to Month 24, subjects will follow the outlined visit schedule (Appendix A to Appendix D) based on treatment assignment (ie, subjects in the monthly groups will be assessed monthly while subjects in the every-other-month [EOM] groups will be assessed every other month). The last visit in the study will be at Month 24, approximately 30 days (monthly treatment group) or 60 days (EOM treatment group) after the last visit at which investigational product is administered. At the end of the 24-month study period, subjects will have the option to enroll into a separate open-label study.

Subjects who discontinue study treatment can continue participation in the study and should be encouraged to return to the clinical site for as many follow-up visits as they can (with the exception of pegcetacoplan/sham administration). Subjects who wish to fully withdraw from the study before Month 24, should be encouraged to complete the early termination visit.

Endpoints and statistical analysis:

Endpoints

Primary Efficacy Endpoint

• Change from baseline to Month 12 in total area of GA lesion(s) in the study eye (in mm²) based on fundus autofluorescence (FAF).

Key Secondary Efficacy Endpoints

- Change from baseline in monocular maximum reading speed (study eye), as assessed by MNREAD or Radner Reading Charts at Month 24 (in select countries)

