7.3. Dosage and Administration

7.3.1. Dose Levels and Treatment Arms

After randomization and during the treatment phase beginning at Day 1, all subjects will receive a single dose of 15 mg pegcetacoplan/0.1 mL or sham injection intravitreally either monthly or every other month depending on treatment designation as presented in Table 1 below.

Table 1: Treatment Arms with Approximate Number of Subjects

Treatment Arms Pegcetacoplan 15 mg/0.1 mL monthly for 24 months (n= approximately 200 subjects; 24 pegcetacoplan injections)

Pegcetacoplan 15 mg/0.1 mL EOM for 24 months (n= approximately 200 subjects; 12 pegcetacoplan injections)

Sham monthly for 24 months (n= approximately 100 subjects; 24 sham injections)

Sham EOM for 24 months (n= approximately 100 subjects; 12 sham injections)

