#### **6.2.3.2. Other Sensitivity Analyses**

The primary endpoint will also be analyzed without pooling the two sham arms (SM and SEOM). The comparison for pegcetacoplan and sham injection within each dose schedule (i.e., PM vs SM and PEOM vs SEOM, respectively) will be conducted using the MMRM analyses described in Section 6.2.2.

The primary endpoint will also be summarized excluding GA total area assessments with an indeterminate boundary. The summary and presentation of the observed values for the total area of GA lesion(s) by treatment group and visit described in Section 6.2.2 will be repeated. The summary and presentation of the analysis results for all timepoints described in Section 6.2.2 will be repeated.

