### 7.1. Adverse Events

AEs will be coded using the MedDRA version 23.1 and summarized separately for those occurred in the study eye, those in the fellow eye, and the non-ocular events.

An AE will be considered a TEAE if it has a start date on or after the first dose of investigational product or if it has a start date before the date of the first dose of investigational product but increases in severity on or after the date of the first dose of investigational product.

An overall summary of the number of subjects with TEAEs will be presented, including the number and percentage of subjects with:

- Any TEAEs
- TEAEs related to study drug (evaluated by the investigator as definitely related, possibly related)
- TEAEs related to study drug injection procedure
- All TEAEs by maximum severity
- Serious TEAEs
- Serious TEAEs related to study drug (evaluated by the investigator as definitely related, possibly related)
- Serious TEAEs related to study drug injection procedure
- Serious TEAEs by maximum severity
- TEAEs leading to interruption of study treatment
- TEAEs leading to discontinuation of study treatment
- TEAEs leading to study discontinuation
- TEAEs leading to death

This overall summary will also include the total number of TEAEs reported. This overall summary will also be summarized separately for those occurred in the study eye, those in the fellow eye, and the non-ocular events.

The number and percentage of subjects reporting TEAEs in each treatment group and overall will be tabulated by SOC and PT for all of the categories in the list above. If more than 1 AE occurs with the same preferred term for the same subject, then the subject will be counted only once for that preferred term using the most severe and most related occurrence for the summarization by severity and by relationship to investigational product.

Endophthalmitis and intraocular inflammation ocular TEAEs will be presented by PT for study eye and fellow eye.

Endophthalmitis and intraocular inflammation ocular TEAEs in the study eye will also be presented on a per-injection basis (i.e., number of events/total number of injections given).

All SOC and PT summaries will be ordered alphabetically by SOC and within SOC, by descending order of the total number of subjects in the PM, PEOM, and Sham groups combined.

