## **7.8. Immunogenicity**

Immunogenicity data will be listed separately for anti-pegcetacoplan peptide antibody and anti-PEG antibody results. The number and percentage of samples confirmed positive for ADA response will be summarized by treatment groups (i.e., PM, PEOM, and Sham). The number and percentage of subjects with treatment-emergent and treatment-boosted responses will be presented by treatment group. Treatment emergent response is defined as a confirmed positive antibody result postdose after a negative antibody result reported at baseline. Treatment-boosted response is defined as a  $\geq 4$ -fold increase in titer from the baseline level.

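### The safety tables set both pegcetacoplan regimens against one pooled sham group that matches neither schedule; SM and SEOM columns would give a like-for-like comparator for events that accumulate with shared procedure steps or visits

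*SAP*

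**What the plan says.** SAP 4 sets the comparator for everything that follows: "Two sham treatment arms (SM and SEOM) will be pooled into a single control (Sham) group for analyses". The safety sections follow suit. SAP 7.1 orders the adverse event tables "by descending order of the total number of subjects in the PM, PEOM, and Sham groups combined", and SAP 7.8 says antibody-positive samples "will be summarized by treatment groups (i.e., PM, PEOM, and Sham").

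The sham arms are unpooled only for efficacy. SAP 6.2.3.2 says "The primary endpoint will also be analyzed without pooling the two sham arms (SM and SEOM"), and SAP 6.3.3 does the same for the key secondary endpoints over 24 months.

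Protocol 7.3.1, Table 1, gives the planned exposure: PM "n= approximately 200 subjects; 24 pegcetacoplan injections"; PEOM "n= approximately 200 subjects; 12 pegcetacoplan injections"; sham monthly about 100 subjects and 24 sham procedures; and "Sham EOM for 24 months (n= approximately 100 subjects; 12 sham injections"). All arms are seen monthly in Year 1. In Year 2, "subjects in the monthly groups will be assessed monthly while subjects in the every-other-month [EOM] groups will be assessed every other month".

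TEAEs, including those attributed to the injection procedure, are reported as counts and percentages of subjects (SAP 7.1). A per-injection rate is specified only for endophthalmitis and intraocular inflammation in the study eye. Exudative AMD also has a rate per 100 subject-years (SAP 7.1.1). IOP above threshold is summarised by timepoint and also cumulatively over the study (SAP 7.5).

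Some text sits uneasily with pooled-only safety tables. SAP 4.4 refers to a corresponding sham arm when it assigns subjects who received a wrong injection. SAP 5.6 gives exposure bands separately for the Monthly and EOM schedules. Protocol 12.6 mentions pooling in the ITT definition but not in the safety set, and Protocol 12.8 says AE summaries are shown for each treatment group separately. SAP 15 does not list safety pooling among the changes from the protocol. None of this specifies SM and SEOM columns for adverse events.

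**The concern.** The design randomises two sham arms whose schedules match the two active regimens. Pooling them is reasonable for lesion area, which neither sham schedule should alter. It is less suitable for a per-subject incidence that rises with the number of procedures or visits, because the pooled group then has fewer opportunities for an event than PM and more than PEOM.

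The exposed outputs are:

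- events from steps that sham and active procedures share (preparation, anaesthesia, and the reporting of procedure-related AEs);
- events that depend on visit frequency (transient findings, AE elicitation, cumulative IOP-threshold counts).

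The safety objective in both documents is comparison with sham. For these outputs, each regimen's contrast with sham mixes a drug effect with a schedule effect, and the schedule effect has opposite signs for the two regimens. Treatment frequency is also known for each subject (SAP 3.3), so only a schedule-matched sham arm balances that knowledge when events are reported.

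**Working it through.** **1. Reproduce the planned counts from the visit schedules (Protocol Appendices A to D).**

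- Monthly: Day 1 and Months 1–12 (13), plus Months 13–23 (11) = 24.
- EOM: Day 1 and Months 2, 4, …, 12 (7), plus Months 14, 16, …, 22 (5) = 12.

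Both agree with Table 1.

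**2. Average for pooled sham.**

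- Procedures: (100 × 24 + 100 × 12) / 200 = 18. PM/sham = 24/18 = 1.33; PEOM/sham = 12/18 = 0.67.
- Year 2 visits (Protocol 8.1.3.2.1: Visits 15–26 against 15–20): 12 and 6, so pooled sham averages 9.
- All visits after Day 1: 24 and 18, so pooled sham averages 21. Ratios 24/21 = 1.14 and 18/21 = 0.86.

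**3. Events from shared procedure steps, no drug effect.** Assume risk p per procedure, equal in all arms, independent across procedures, with full exposure. The incidence with k procedures is 1 − (1 − p)^k; pooled sham is the mean of k = 24 and k = 12. The documents give no p, so a range is shown.

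| p | PM | Pooled sham | PEOM | RR PM | RR PEOM | Difference (points) |
|---|---|---|---|---|---|---|
| 0.1% | 2.4% | 1.8% | 1.2% | 1.33 | 0.67 | ±0.6 |
| 1% | 21.4% | 16.4% | 11.4% | 1.31 | 0.69 | ±5.0 |
| 3% | 51.9% | 41.2% | 30.6% | 1.26 | 0.74 | ±10.6 |

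Against SM and SEOM the expected ratio is 1.00 in both comparisons. Before the Month 12 injection the counts are 12 and 6 (pooled 9), and the same formula gives 1.33/1.32/1.29 for PM and 0.67/0.68/0.71 for PEOM.

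**4. Transient findings seen only at visits.** Assume a chance q per visit of 0.1% to 5%, with 24 against 18 visits. At q = 1%: 1 − 0.99^24 = 21.4%, 1 − 0.99^18 = 16.6%, pooled 19.0%; ratios 1.13 and 0.87. Over the range: 1.14 to 1.08 for PM and 0.86 to 0.92 for PEOM.

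**5. Events caused by the needle or volume.** Sham involves no needle entry (Protocol 7.4). Assume 1% risk per active and 0.1% per sham procedure: PM 21.43%, SM 2.37%, PEOM 11.36%, SEOM 1.19%, pooled sham 1.78%.

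- PM: 21.43 − 2.37 = 19.06 points matched; 21.43 − 1.78 = 19.65 pooled.
- PEOM: 11.36 − 1.19 = 10.17 matched; 11.36 − 1.78 = 9.58 pooled.

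The shift is about 0.6 points each way. A ratio still moves because its denominator is small (PM 9.0 matched, 12.0 pooled), but SAP 7 plans percentages rather than ratios. If sham risk is zero, pooling changes nothing.

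**6. Precision cost of matching.** The comparator falls from about 200 to about 100 subjects. At similar event proportions the standard error ratio is √[(1/200 + 1/100) / (1/200 + 1/200)] = √1.5 = 1.22.

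**The case against.** Much of the case for leaving the tables alone is sound, and it narrows the point.

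- **Sham is not an injection.** The equal-risk figures in step 3 cannot be applied to all injection-related events. A reader might take the ±5 points at p = 1% as the general size of the problem. The documents do not support that, because needle- and volume-caused events cannot arise in either sham arm.
- **Not every ocular output accumulates with visits.** Slit-lamp and ophthalmoscopy shifts are shown at Month 12, Month 24 and last observed value (SAP 7.5), and the two fixed visits occur in every arm. IOP thresholds also have a by-timepoint summary. Routine IOP measurement after injection is not required: it follows a failed gross vision test or same-day anti-VEGF treatment (Protocol 9.15).
- **CNV.** A reader might infer that exudative AMD incidence is inflated for PM in proportion to visits. CNV that persists is still looked for by SD-OCT and FFA at Month 24 in every arm, so fewer visits mainly delay detection.
- **Year 1 visits are equal** under the standard schedule. The exception is the COVID-19 minimum schedule, which lets EOM subjects skip non-dosing visits. The Month 12 report is therefore exposed mainly through procedure counts.
- **Some adjustment exists.** Besides the two rates already described, SAP 5.6 tabulates total injections to support per-injection TEAE rates. It does not extend those rates to other injection-procedure events, and subject-years do not adjust for visit or procedure frequency.
- **More procedures are a real burden of monthly treatment.** That is true, and a matched comparison deliberately removes it to isolate the drug effect. The pooled group does not measure that burden cleanly either, because its schedule is that of neither regimen.

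What remains is that, for the outputs still exposed, no like-for-like comparator is specified although the trial randomises one.

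**Conclusion.** The point holds in a limited form. Pooled sham gives PM and PEOM a mismatched comparator for events from shared procedure steps and for events whose capture depends on visit frequency. The counts are exact. The sizes are illustrative: risk ratios of 1.33 to 1.26 and 0.67 to 0.74 rest on equal risk per shared step of 0.1% to 3%, independence and full exposure. The visit effect is smaller and, under the standard schedule, comes only from Year 2.

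Two further inferences should be resisted. Pooling sham does not alter the direct PM versus PEOM contrast, since those columns are the same either way; what it alters is each regimen's contrast with sham. Nor is any type I error affected, because SAP 7 specifies descriptive AE summaries and no safety hypothesis test; the risk ratios above are constructed here to show size.

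This is a cheap improvement to the presentation of safety data, not a flaw that invalidates it.

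**What to change.** In SAP 7, keep the pooled Sham column and add SM and SEOM columns to:

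- the TEAE overview;
- injection-procedure TEAEs;
- study-eye ocular TEAEs by preferred term;
- IOP-threshold incidence over the whole study;
- the exudative AMD incidence and Kaplan-Meier outputs.

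Name PM vs SM and PEOM vs SEOM as the schedule-matched comparisons for these tables. Reconcile SAP 4 with the reference to a corresponding sham arm in SAP 4.4 and with the by-group AE presentation in Protocol 12.8, and record the safety pooling in SAP 15 if it is retained.

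The cost is two extra columns per table. Each sham column holds about 100 subjects, so risk-difference intervals against matched sham are about 22% wider; the pooled column stays for precision on rare events.
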